4.2. End of Trial Definition

End of the trial is the date of the last visit or last scheduled procedure shown in the Schedule of Activities (Appendix 2) for the last patient.

4.3. Scientific Rationale for Study Design

The length of the randomized, double-blind treatment phase (3 months) is considered a sufficient duration to assess the safety and efficacy of a migraine prevention medication given the mechanism and observed onset of action for CGRP antibodies (Dodick et al. 2014a, 2014b). Furthermore, a placebo-controlled study with a duration longer than 3 months may not be tolerated by patients suffering from chronic migraine. A 4-month post-treatment follow-up phase is included to evaluate patient safety during wash-out of LY2951742. This allows for a total of 5 months of observation from the time of last injection of LY2951742. A 5 -month post-treatment observation period allows for a wash-out of approximately 5 elimination half-lives of LY2951742 and should decrease LY2951742 serum concentrations by approximately 97% during this time.

4.4. Justification for Dose

Doses of 120 mg and 240 mg administered once monthly were selected primarily on the basis of clinical efficacy and pharmacokinetic/pharmacodynamic data from the Phase 2 dose-ranging study. Results from the dose-ranging study indicate that 120 mg was statistically significantly superior to placebo at the last 28-day period of the 3-month treatment phase in mean change in migraine headache days, as well as other measures of efficacy and quality of life. The use of a loading dose for the 120 mg treatment arm, and the inclusion of a 240 mg treatment arm, is based on the finding that a dose higher than 120 mg achieved statistically significant separation from placebo as early as Month 1. The doses of 120 mg and 240 mg LY2951742 planned for Study CGAI also are being evaluated in two other pivotal efficacy studies of LY2951742 (both in patients with episodic migraine).

4.5. Benefit/Risk Assessment

More information about the known and expected benefits, risks, serious adverse events (SAEs) and reasonably anticipated adverse events (AEs) of LY2951742 are to be found in the Investigator's Brochure (IB).

5. Study Population

All patients must meet the following selection criteria. Eligibility of patients for study enrollment will be based on the results of a screening medical history, physical examination, neurological examination, clinical laboratory tests, electrocardiograms (ECGs), and migraine history during screening and the prospective baseline period, as described in the Inclusion and Exclusion Criteria sections. The nature of any comorbid conditions present at the time of the physical examination and any preexisting conditions must be documented. Individuals who do not meet the criteria for participation in this study (screen failure) for specific reasons as outlined may be considered for re-screening once, with approval from Eli Lilly and Company (Lilly) Medical (Section 5.3).

Study participants should be instructed not to donate blood or blood products during the study or for 5 months following the last administration of investigational product.

Prospective approval of protocol deviations to recruitment and enrollment criteria, also known as protocol waivers or exemptions, are not permitted.

5.1. Inclusion Criteria

Patients are eligible to be included in the study only if they meet all of the following criteria at screening:

Patient and Disease Characteristics

- [1] Patients are 18 to 65 years of age (inclusive) at the time of screening.
- [2] Have a diagnosis of chronic migraine as defined by the IHS ICHD-3 beta guidelines (1.3) (ICHD-3 2013), that is, a headache occurring on 15 or more days per month for more than 3 months, which has the features of migraine headache on at least 8 days per month.
- [3] Migraine onset prior to age 50.
- [4] Prior to Visit 1, a history of at least 1 headache-free day per month for the past 3 months.
- [5] From Visit 2 to Visit 3 (prospective baseline period), have a frequency of at least 15 headache days, of which at least 8 must have the features of migraine headache (see definitions in Table CGAI.2). To avoid biased reporting, patients must not be told the number of migraine headache days on which study qualification is based.
- [6] From Visit 2 to Visit 3 (prospective baseline period), have at least one headache-free day.
- [7] From Visit 2 to Visit 3 (prospective baseline period), must achieve sufficient compliance with ePRO daily headache entries as demonstrated by completion of at least 80% of daily diary entries.

Informed Consent and Patient Agreements

- [8] Are able and willing to give signed informed consent.
- [9] Are reliable and willing to follow study procedures, including all follow-up visits.
- [10] Women of child-bearing potential must test negative for pregnancy at the time of enrollment based on a serum pregnancy test.
- [11] All patients, male and female, must agree to use a reliable method of birth control during the study as well as for 5 months after the last dose of investigational product. Acceptable methods of birth control for this study include: oral contraceptives; implantable contraceptives; injectable contraceptives; a contraceptive patch; barrier methods such as diaphragms with contraceptive jelly, cervical caps with contraceptive jelly, condoms with contraceptive foam, or intrauterine devices; a partner with vasectomy. Birth control is not required if the female is infertile due to surgical sterilization (at least 6 weeks after surgical bilateral oophorectomy, hysterectomy, or at least 6 weeks after tubal ligation) confirmed by medical history, or menopause. Menopause is defined as spontaneous amenorrhea for at least 12 months not induced by a medical condition, or spontaneous amenorrhea of 6-12 months and a follicle stimulating hormone level >40 mIU/mL.
- [12] Agree not to post any personal medical data related to the study or information related to the study on any website or social media site (for example, Facebook, Twitter, LinkedIn, Google+, etc.) until the entire trial has completed.

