To compare LY2951742 with placebo with respect to 50% response rate	• The proportion of patients with reduction from baseline ≥50% in monthly migraine headache days during the 3-month double-blind treatment phase
To compare LY2951742 with placebo with respect to 75% response rate	The proportion of patients with reduction from baseline ≥75% in monthly migraine headache days during the 3-month double-blind treatment phase
To compare LY2951742 with placebo with respect to 100% response rate	The proportion of patients with reduction from baseline of 100% in monthly migraine headache days during the 3-month double-blind treatment phase
To compare LY2951742 with placebo with respect to change in functioning	Mean change from baseline in the Role Function- Restrictive domain score of the Migraine-Specific Quality of Life Questionnaire version 2.1 (MSQ v2.1) at Month 3

Objective(s)/Endpoints:

Obj	ectives	Endpoints
	To compare LY2951742 with placebo with respect to change in use of acute (abortive) migraine treatment	The overall mean change in the number of monthly migraine headache days requiring medication for the acute treatment of migraine or headache during the 3-month double-blind treatment phase
	To compare LY2951742 with placebo with respect to change in global severity of the migraine condition	The mean change from baseline in the Patient Global Impression of Severity (PGI-S) score at Month 3

Summary of Study Design:

A multisite, randomized, double-blind, parallel, placebo-controlled trial with 5 study periods in patients who meet International Classification of Headache Disorders (ICHD) criteria for a diagnosis of chronic migraine as confirmed during a prospective baseline period.

Treatment Arms and Duration:

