^a The eligibility period of the prospective baseline assessment will last from 30 to 40 days. Investigators and patients may have up to an additional 5 days to schedule their Visit 3 appointment (beyond the 40 days); however, eligibility will be based on the 30- to 40-day period.

^b Visit is to include a review of any spontaneously reported adverse events and collection of blood samples for immunogenicity, PK, and CGRP plasma.

^c A neurological exam will be conducted at screening, Month 3 (final visit of double-blind treatment), Months 6, 9, and 12 (open-label treatment), and Month 16/early termination in order to assess for any signs of pre-existing or treatment-emergent neurological abnormalities such as stroke or other cerebrovascular events.

^d Electrocardiograms (ECGs) will be performed at Visit 1, Visit 3, Visit 7, Visit 10, Visit 16, and Visit 18 or early termination. Note: The Visit 3 ECG should be collected prior to blood draws and dosing. Patients must be supine for approximately 5 to 10 minutes before ECG collection and remain supine but awake during ECG collection.

^e Vital signs taken at every office visit will include body temperature, blood pressure and pulse. Blood pressure and pulse will be measured in triplicate in the sitting position and should be measured prior to blood draws. Blood pressure will be assessed by utilizing a calibrated machine.

^f Chemistry labs collected at Visit 3, Visit 7, Visit 10, Visit 13, Visit 16, and Visit 18 or early termination must be fasting. Fasting is defined as no food or drink, except water, for at least 8 hours prior to testing.

g In the event of a positive urine leukocyte esterase result, a repeat urine sample will be collected and shipped to the central laboratory.

^h A positive urine test must be followed by a serum pregnancy test for confirmation.

Immunogenicity and storage sample, and PK blood sampling to be performed at the indicated visits and prior to dose administration if the visit is a dosing visit. Samples will be taken in the event of early termination. Immunogenicity samples also may be collected in the event of a systemic allergic/hypersensitivity reaction (see Section 8.4.3). The exact date and time of the samples should be recorded.

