The daily data will reflect whether the patients meet the migraine / probable migraine criteria; those data will be aggregated, and the number of migraine headache days will be provided for each of the 30-day periods. In calculating the number of migraine headache days for each period, if the period is not equal to 30 days, the number of migraine headache days will be adjusted by multiplying the number of migraine headache days by (30/x) where 'x' is the total number of non-missing diary days in the period.

For the 4 months of post-treatment period, the monthly intervals will be derived as below:

- Firstly, the 2-month visit interval will be split into two 1-month periods for efficacy measures. If the number of days between 2 visits (visit x+1 date visit x date + 1) is even, the first half will be in the first 1-month period and the second half will be in the second 1-month period. If the number of days between 2 visits is odd, then the days will be split similarly, but the first 1-month period will have 1 day more than the second 1-month period.
- Secondly, after the 2-month visit intervals are split into two 1-month periods, the monthly data will be derived in the same way for each 1-month period as for treatment phase. For patients who discontinued early during post-treatment phase (Study Period V [SP V]), if the date of discontinuation is within 30 days of the previous visit date, all data between the previous visit date and the discontinuation date will go to 1 monthly period; if the date of discontinuation is more than 30 days of the previous visit date, then the first 30 days will be the first monthly period, and the rest will be considered as part of the second monthly period.

This approach to missing ePRO diary data assumed that the rate of migraine headache per day is the same for days with missing and nonmissing ePRO diary days. The same approach will also be applied to secondary and exploratory efficacy measures that are derived from ePRO data.

Additionally, if the compliance rate for a monthly interval is \leq 50%, then all endpoints to be derived from the ePRO diary data for that 1-month period will be considered missing.

For the post-treatment phase, the derived 1-month periods (resulting from splitting the 2-month visit interval) will be treated similarly.

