Appendix Table 1. Description of Important Protocol Deviations

Category	Subcategory	Study-specific	Source	Methods of Identification
Informed Consent	ICF not obtained	Initial ICF date is missing or is after (Visit 1 date or Visit 1 lab date)	Programmable - Stats	For all patients, if initial ICF date is missing or after (Visit 1 date or Visit 1 lab date).
Form (ICF)	Improper ICF	ICF not signed prior to initiation of protocol procedures	Non-programmable - Monitor identified	Or determined by study team
		Age <18 or >65 years old at study entry	Non-programmable- Monitor identified	
		BMI ≥40 at baseline	Programmable - Stats	
		Do not meet criteria of at least 15 normalized headache days of which 8 must have features of migraine	Programmable - Stats	Number of normalized headache days <15, or number of normalized migraine headache days < 8
	leal along	At least one headache free day	Programmable - Stats	Number of normalized headache days > 29
Eligibility	Inclusion/ Exclusion	Baseline ePRO compliance <80%	Programmable - Stats	
		Female patients who have a positive serum pregnancy test prior to randomization visit	Programmable - Stats	For randomized female patients, if serum pregnancy test is positive any time prior to Visit 3
		Female patients who have a positive or no serum pregnancy test prior to randomization visit	Non-programmable- Monitor identified	
		Insufficient washout of prohibited migraine preventive medication for at least 30 days prior to Visit 2	Programmable - Stats	Patients must have discontinued such treatment at least 30 days prior to Visit 2.

Category	Subcategory	Study-specific	Source	Methods of Identification
		Insufficient washout of Botulinum toxin A and B at least 4 months prior to Visit 2	Non-programmable- Study team identified	Stats will create the list of patients meet this IPD criteria. Among those, the true IPDs will be manually added into non-programmable excel sheet
		With suicidal ideation (Q4 or Q5) within past month of visit 1.	Programmable - Stats	Randomized patients with answer "yes" for C-SSRS suicidal ideation Q4 or Q5 occurred within past 1 month of visit 1.
		Positive or no urine drug screen prior to randomization	Programmable - Stats	For randomized patients if prior to visit 3, a patient has a positive UDS result and a repeated UDS not done or last repeat UDS is positive or UDS never collected.

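### Inclusion criterion 5 sets 15 headache and 8 migraine days over a 30- to 40-day baseline with no 30-day denominator, while the SAP checks the same thresholds on counts scaled to 30 days, so the two rules can disagree in both directions

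*Protocol*

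**What the plan says.** Protocol 5.1, criterion 5, asks that patients, from Visit 2 to Visit 3, "have a frequency of at least 15 headache days, of which at least 8 must have the features of migraine headache". Criterion 7 accepts 80% diary completion over the same period. Criterion 2 gives the disease definition as a monthly rate, "a headache occurring on 15 or more days per month for more than 3 months", with at least 8 migraine days per month. The protocol synopsis describes the diagnosis "as confirmed during a prospective baseline period".

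The length of that period varies. Footnote a to Protocol Appendix 2 says: "The eligibility period of the prospective baseline assessment will last from 30 to 40 days". It allows up to 5 more days to schedule Visit 3, but "eligibility will be based on the 30- to 40-day period".

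SAP 5.4.1 scales diary counts to 30 days: "the number of migraine headache days will be adjusted by multiplying the number of migraine headache days by (30/x"). The divisor counts only days on which a diary entry was made. The section applies the same approach to headache days. SAP Appendix Table 1 then programs the important deviation for criterion 5 as: "Number of normalized headache days <15, or number of normalized migraine headache days < 8".

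**The concern.** One criterion has two counting rules. As written, criterion 5 is a count over whatever window the patient had. Its meaning as a monthly rate falls as the window lengthens and rises as diary days are missed. The SAP rule holds the monthly rate fixed. No section reconciles them.

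The primary objective is a claim in chronic migraine, and the prospective baseline is the step that confirms the diagnosis. If the eligibility notice sent to sites (Protocol 4.1, Study Period II) follows criterion 5 literally, two things can happen. Patients whose baseline lies below the monthly frequency in criterion 2 can be randomized and then listed as important deviations, and some patients with permitted missed diary days are refused. If the notice normalizes, no one is misclassified, but criterion 5 misstates the rule in use. Protocol section 5 allows no eligibility waivers, so the criterion should have one reading.

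**Working it through.** The plan states no figure to reproduce, so the check applies the SAP formula to the protocol thresholds.

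**Inputs.** Thresholds of 15 and 8 and minimum completion of 80% (Protocol 5.1); window of 30 to 40 days (Protocol Appendix 2, footnote a); scaling 30/x (SAP 5.4.1). The SAP sentence is conditioned on the period not being 30 days, but the section goes on to present it as its approach to missing diary data. I therefore apply it whenever x differs from 30.

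**Formulas.** Normalized days = counted days × 30/x. Count needed to pass the SAP check = 15x/30 for headache and 8x/30 for migraine, rounded up.

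| Window, diary | x | 15 headache days per 30 | 8 migraine days per 30 | Count needed for SAP (headache / migraine) |
|---|---|---|---|---|
| 30 days, complete | 30 | 15.0 | 8.0 | 15 / 8 |
| 35 days, complete | 35 | 12.86 | 6.86 | 18 / 10 |
| 40 days, complete | 40 | 11.25 | 6.0 | 20 / 11 |
| 40 days, 80% | 32 | 14.06 | 7.5 | 16 / 9 |
| 30 days, 80% | 24 | 18.75 | 10.0 | 12 / 7 |

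At x = 30 the two rules coincide, as they should.

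**Meets criterion 5, flagged by the SAP.** With 40 complete diary days, 15 to 19 headache days meet the headache threshold but normalize to 11.25 to 14.25 (19 × 30/40), all below 15. Likewise 8 to 10 migraine days normalize to 6.0 to 7.5 (10 × 30/40), all below 8.

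**Fails criterion 5, not flagged.** With 24 of 30 diary days completed, 13 headache days normalize to 13 × 30/24 = 16.25, and 7 migraine days to 7 × 30/24 = 8.75. Both fall short of the protocol counts and both pass the SAP check.

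**Illustration of size.** Assume independent days with a constant rate, consider the headache threshold only, and ignore screening under criterion 2. These are my assumptions. The chance of passing is a binomial tail.

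| True rate per 30 | x | Unscaled count ≥15 | Normalized ≥15 |
|---|---|---|---|
| 12 | 30 | 0.175 | 0.175 |
| 12 | 40 | 0.683 | 0.130 |
| 12 | 32 (80% of 40) | 0.268 | 0.165 |
| 16 | 24 (80% of 30) | 0.245 | 0.703 |

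**Related check.** Criterion 6 requires one headache-free day. SAP Appendix Table 1 flags more than 29 normalized headache days. One headache-free day in 40 gives 39 × 30/40 = 29.25, so a patient who meets criterion 6 is flagged. In a complete 30-day window the value is exactly 29 and is not flagged.

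**The case against.** The best defence is that criterion 5 never says its count is unscaled. It speaks of a frequency, the disease is defined per month a few lines above, and Protocol 9.2 and 9.3.2 and SAP 5.3 and 5.5.4 all describe a 30-day baseline. The SAP's own restatement of the criterion in terms of normalized days suggests that normalization was intended. Sites do not count days; they are told whether the patient qualified. On this view a phrase is missing and nothing went wrong in practice. That may be so, and it is why the consequences must be stated conditionally. It does not remove the need for correction, because the only period criterion 5 names is not 30 days long and the rule behind the notice is not given.

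Long windows and missed days also partly offset each other. At 80% completion of 40 days, 15 headache days is 14.06 per 30, and the gap in pass probabilities shrinks to 0.268 against 0.165. This stands: the 40-day complete diary and the 30-day diary at 80% are corner cases, and the documents give no distribution of either quantity.

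A reader might infer three stronger things that the documents do not support.

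- That the trial enrols patients with episodic migraine. Criterion 2 separately requires chronic migraine by history, so a low count in one window does not show that the diagnosis is absent.
- That the count may run over 45 days because criterion 5 extends to Visit 3. Footnote a restricts eligibility to the 30- to 40-day period.
- That the efficacy comparison is compromised. The criterion is applied before randomization, and patients are analysed as randomized. SAP 5.5.1.4 defines no per-protocol population, and SAP 5.5.3 only summarizes and lists deviations.

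**Conclusion.** The inconsistency is real and should be corrected. Criterion 5 and the SAP check agree with certainty only when there are 30 non-missing diary days. Away from that they can disagree in either direction: at the extremes, the protocol's 15 headache days correspond to 11.25 per 30 (40 diary days) or 18.75 per 30 (24 diary days).

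The textual mismatch rests on no assumption beyond reading criterion 5 as written. Whether any patient was wrongly admitted, refused or flagged depends on the algorithm behind the eligibility notice and on actual window lengths and completion, none of which the documents give. The pass probabilities are illustrations, not estimates for this trial. The effect is confined to who is enrolled, how that population is described, and how far the deviation listing can be trusted.

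**What to change.** Reconcile Protocol 5.1 and Appendix 2 footnote a with SAP 5.4.1 and Appendix Table 1:

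- State criterion 5 as at least 15 headache days and at least 8 migraine days per 30 days over the 30- to 40-day eligibility period, each calculated as days × 30 / non-missing diary days.
- Confirm that the electronic diary's eligibility notice uses this formula, and run the SAP check on the same days, without the extra scheduling days. If enrolment is already complete, document the rule actually used and align the deviation listing with it.
- State whether probable migraine counts toward the 8 days. The SAP term for migraine headache days includes it; criterion 5 speaks only of migraine features.
- Align the SAP check of criterion 6 with the criterion, so that one headache-free day is judged the same way whatever the window length.

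The cost is a sentence in the criterion, small edits to the deviation table and one check of the algorithm. The downside is that some patients with long baselines who qualify on unscaled counts would fail screening, partly offset by patients with permitted missed days who would qualify.

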5.2. Exclusion Criteria

Patients will be excluded from study enrollment if they meet any of the following criteria at screening:

Prior/Concurrent Clinical Trial Experience

- [13] Are currently enrolled in any other clinical trial involving an investigational product or any other type of medical research judged not to be scientifically or medically compatible with this study.
- [14] Have participated within the last 30 days or within 5 half-lives (whichever is longer) in a clinical trial involving an investigational product. If the investigational product's half-life is not known, 6 months should have passed prior to Visit 1.
- [15] Current use or prior exposure to LY2951742 or another CGRP antibody, including those who have previously completed or withdrawn from this study or any other study investigating a CGRP antibody.

Prior/concomitant therapy

- [16] Patients who are taking, or are expected to take, therapeutic antibodies during the course of the study (for example, adalimumab, infliximab, trastuzumab, bevacizumab, etc.). Prior use of therapeutic antibodies, other than antibodies to CGRP or its receptor, is allowed if that use was more than 12 months prior to Visit 2
- [17] Known hypersensitivity to multiple drugs, monoclonal antibodies or other therapeutic proteins, or to LY2951742.
- [18] Are currently receiving a disallowed treatment for the prevention of migraine headaches (anything other than topiramate or propranolol). Patients must have discontinued such disallowed preventive migraine treatment at least 30 days prior to Visit 2. Botulinum toxin A and B that has been administered in the head or neck area must be discontinued at least 4 months prior to Visit 2. Patients who have been on a stable dose of either topiramate or propranolol for at least 2 months prior to Visit 2 may continue to take that preventive medication throughout the trial. Patients may only take one of these 2 allowed prophylactic medications during the trial, and the dose must remain stable throughout the double-blind treatment period.
- [19] Failure to respond to 3 or more adequately dosed migraine preventive treatments from different classes (that is, maximum tolerated dose for at least 2 months). Failure to respond due to tolerability issues is not considered a treatment failure. Migraine preventive treatments are defined as Level A and Level B in Table 1 of the American Academy of Neurology's Evidence-based Guidelines Update: Pharmacologic Treatment for Episodic Migraine Prevention in Adults (Silberstein et al. 2012) as well as botulinum toxin A or B.

Diagnostics Assessments

- [20] History of persistent daily headache, cluster headache or migraine subtypes including hemiplegic (sporadic or familial) migraine, ophthalmoplegic migraine, and migraine with brainstem aura (basilar-type migraine) defined by IHS ICHD-3 beta.
- [21] History of headache other than migraine, tension type headache, or medication overuse headache, as defined by IHS ICHD-3 beta within 3 months prior to randomization.
- [22] History of head or neck injury within 6 months prior to Visit 1.
- [23] Patients with a history of traumatic head injury associated with significant change in the quality or frequency of their headaches should be excluded.

Medical Conditions

- [24] Have ECGs showing abnormalities compatible with acute cardiovascular events and/or serious cardiovascular risk, including but not limited to a corrected QT (QTcB [Bazett's]) interval >470 msec for women and >450 for men, or have had myocardial infarction, unstable angina, percutaneous coronary intervention, coronary artery bypass graft, or deep vein thrombosis/pulmonary embolism within 6 months of screening, or have planned cardiovascular surgery or percutaneous coronary angioplasty, or a lifetime history of stroke.
- [25] Patients with a body mass index $\geq 40 \text{ kg/m}^2$.
- [26] Any liver tests outside the normal range at Visit 1 that are clinically significant. Alanine aminotransferase (ALT) >2X upper limit of normal (ULN), or total bilirubin level (TBL) >1.5X ULN, or alkaline phosphatase (ALP) >2X ULN must be discussed and judged not clinically significant by Eli Lilly and Company (Lilly) Medical prior to enrollment.
- [27] Evidence of significant active or unstable psychiatric disease by medical history, such as bipolar disorder, schizophrenia, personality disorders, or other serious mood or anxiety disorders. Note: Patients with major depressive disorder or generalized anxiety disorder whose disease state is considered stable and expected to remain stable throughout the course of the study, in the opinion of the investigator, may be considered for inclusion if they are not on excluded medications.
- [28] Patients who, in the clinician's judgment, are actively suicidal and therefore deemed to be at significant risk for suicide, or those who have answered "yes" to either Question 4 (Active Suicidal Ideation with Some Intent to Act, Without Specific Plan) or Question 5 (Active Suicidal Ideation with Specific Plan and Intent) on the "Suicidal Ideation" portion of the Columbia Suicide Severity Rating Scale (C–SSRS), or answer "yes" to any of the suicide-related behaviors (actual attempt, interrupted attempt, aborted attempt, preparatory act or behavior) on the "Suicidal Behavior" portion of the C–SSRS; and the ideation or behavior occurred within the past month.
- [29] Women who are pregnant or nursing.
- [30] Patients who have used opioids or barbiturate containing analgesic >3X per month for the treatment of pain in more than 2 of the past 6 months (opioid administration in an emergency setting may be an exception).
- [31] History of drug or alcohol abuse/dependence within 1 year prior to Visit 1 (excessive or compulsive use as judged by the Investigator), or currently using drugs of abuse (including opioids, barbiturates and marijuana), or any prescribed or over-the-counter medication in a manner that the Investigator considers indicative of abuse/dependence.

- [32] Have a positive urine drug screen for any substances of abuse at Visit 1. Note: A retest is allowed if the urine drug screen is positive for any prescribed substance or if, in the judgment of the investigator, there is an acceptable explanation for the positive result. The results of the retest must be negative at or prior to Visit 2.
- [33] Have a history or presence of any other medical illness including but not limited to any autoimmune disease, cardiovascular, hepatic, respiratory, hematological, endocrine, psychiatric or neurological disease, or any clinically significant laboratory abnormality, that in the judgment of the investigator, indicates a medical problem that would preclude study participation.

Other Exclusions

- [34] In the opinion of the investigator, have other issues which would interfere with compliance with the study requirements and completion of evaluations required for this study.
- [35] Are investigator site personnel directly affiliated with this study and/or their immediate families. Immediate family is defined as a spouse, parent, child, or sibling, whether biological or legally adopted.
- [36] Are Lilly employees.
- [37] Are unwilling or unable to comply with the use of a data collection device.

